4.5. Timing of Analyses

A single DMC analysis occurred in September 2022.

A final analysis will be conducted once the database is cleaned and locked.

5. ANALYSIS SETS

The following analysis populations will be defined for this study: Intent-to-Treat Analysis Set and Safety Analysis Set.

5.1. Intent-To-Treat Analysis Set

The Intent-to-Treat (ITT) Analysis Set consists of all subjects who are randomized. The ITT analysis set will be the primary population for efficacy analyses.

5.2. Safety Analysis Set

The Safety Analysis Set consists of all subjects who receive at least one dose of study medication. Subjects in this population will be analyzed according to the treatment they received, regardless of the treatment to which they were randomized. The Safety Analysis Set will be used for all summaries of safety data.

6. STATISTICAL METHODS

Descriptive statistical methods will be used to summarize the data from this study. Unless stated otherwise, the term “descriptive statistics” refers to number of subjects (n), mean, median, standard deviation, interquartile range, minimum, and maximum for continuous data and frequency and percentage for categorical data. The term “treatment group” refers to the randomized assignment: ENTO or placebo. Unless otherwise specified, data summaries and analyses described below will be reported by treatment group. All data collected during the study will be included in data listings. Unless otherwise noted, the data will be sorted first by treatment, patient number, and then by assessment date for each patient number. The number of subjects screened, enrolled, treated, and discontinued from study drug will be summarized along with the primary reason for study treatment discontinuation. The number of subjects in each analysis population will be presented by treatment group.

6.1. Demographics and Baseline Characteristics

Demographic data including age (years), sex, race, ethnicity, geographic region (North America, South America, European Union, Asia Pacific), (height (cm), weight (kg), and body surface area (m²) will be summarized for the ITT Analysis Set.

All information pertaining to AML diagnosis as collected on the eCRF will be listed.

6.2. Medical History

All clinically relevant prior or concurrent medical conditions will be mapped to system organ class (SOC) and PT using the version of Medical Dictionary for Regulatory Activities (MedDRA) in effect at the time of database lock. The number and percent of subjects in the ITT Analysis Set reporting each medical condition will be summarized according to SOC and PT.

All medical history will be listed.

6.3. Exposure to Treatment

The number of days on oral study drug and cumulative dose will be summarized by treatment group for the Safety Analysis Set. Additionally, the number of chemotherapy cycles completed and the relative dose intensities for each chemotherapy agent will be presented by treatment group, separately for Induction and Consolidation and presented by cycle and overall. Drug administration details will be listed.

6.4. Efficacy

No analysis of protocol defined primary or secondary efficacy endpoints will be generated. A summary of the investigator assessment of response after two cycles of chemotherapy will be summarized by treatment group for the Safety Analysis Set as this analysis was previously generated for the DMC.

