 - ◆ For categorical variables that are presented in frequency tables, the module should present the total count in addition to the count in each category. Percentages should be calculated using this total as the denominator, and the percentage corresponding to the sum itself (that is, 100%) should be presented so as to indicate clearly to a reviewer the method of calculation.
- Sorting: Listings will be sorted by treatment group, patient number, and date, if applicable. If a listing is sorted in a different manner, a footnote will indicate as such.

- General formatting rules: Rounding for all variables will occur only as the last step, immediately prior to presentation in listings, tables, and figures. No intermediate rounding will be performed on derived variables. The standard rounding practice of rounding numbers ending in 0-4 down and numbers ending in 5-9 up will be employed.
- The presentation of numerical values will adhere to the following guidelines:
 - ◆ Raw measurements will be reported to the number of significant digits as captured electronically or on the CRFs.
 - ◆ Standard deviations will be reported to two decimal places beyond the number of decimal places the original parameter is presented.
 - ◆ Means, medians, first and third quartiles will be reported to one decimal place beyond the number of decimal places the original parameter is presented.
 - ◆ Calculated percentages will be reported with no decimals.
- Dates will be formatted as DDMMYY YYYY. Partial dates will be presented on data listings as recorded on CRFs.
 - Time will be presented according to the 24-hour clock (HHMM).

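### The SAP's only efficacy summary table sits on the Safety Set, with its grouping and its handling of unassessed subjects unsettled, so its response rates need not be responders over randomised subjects

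*SAP*

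**What the plan says.** SAP 6.4 drops all analyses of the protocol's primary and secondary efficacy endpoints and keeps one summary: "A summary of the investigator assessment of response after two cycles of chemotherapy will be summarized by treatment group for the Safety Analysis Set". The reason given is "as this analysis was previously generated for the DMC". In the output list (SAP Section 10) this is Summary Table 4, with Listing 6 showing the same assessments by subject.

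Other parts of the SAP bear on that table:

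- **Population.** SAP 5.1: "The ITT analysis set will be the primary population for efficacy analyses". SAP 5.2: "The Safety Analysis Set consists of all subjects who receive at least one dose of study medication", and "The Safety Analysis Set will be used for all summaries of safety data".
- **Grouping.** SAP 5.2: "Subjects in this population will be analyzed according to the treatment they received, regardless of the treatment to which they were randomized". SAP Section 6, however, says that the term treatment group "refers to the randomized assignment: ENTO or placebo".
- **Denominator.** Appendix A allows subjects with missing values to be left out of a summary module. For categorical variables the module shows a total count, and "Percentages should be calculated using this total as the denominator".
- **Missing data.** SAP 4.4.6 sends the reader to 6.4 for imputing missing efficacy endpoints and otherwise imputes nothing. Section 6.4 contains no imputation rule.

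The protocol's original approach differed. Sections 9.4.2.1 and 9.4.2.2 analyse the primary endpoint on ITT, count deaths before the end of Chemotherapy Cycle 2 as not achieving it, and impute missing MRD as failure. Section 9.4.3 says categorical secondary endpoints are analysed similarly. CR rate after two cycles, by investigator assessment, is one of them.

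**The concern.** The SAP states a population for efficacy and then presents its one efficacy summary table on a different set. That leaves the ITT rule with no efficacy table to govern. The stated reason explains why the table exists, but not why a table in the clinical study report should take its population from a monitoring output.

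Two further gaps affect what is printed. Section 6.4 asks for a summary by treatment group on the Safety Set, which invokes two definitions of grouping at once, so a programmer cannot tell which applies. And nothing says where a subject without a post-Cycle 2 assessment goes. Under the general convention that subject can disappear from both the categories and the total.

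No testing is planned, so the displayed percentages are what a reader will take away. With arms this small, one subject more or less in a denominator changes a percentage visibly.

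**Working it through.** The plan gives no figure for this table, so there is nothing to reproduce. The check has two parts.

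**1. The rules read together**

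- *Membership.* ITT and the Safety Set differ only by subjects randomised but never given study medication. Their number is not stated.
- *Grouping.* The as-treated and as-randomised versions differ only if someone received the other arm's medication. No such case is reported.
- *Denominator.* Appendix A permits omission of missing values, 4.4.6 imputes nothing by default, and 6.4 adds no rule and lists no response categories. An unassessed subject is therefore in the denominator only if the table shell has a row for that status. The SAP specifies none.

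**2. What dropping subjects does to a rate**

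Let N be the subjects randomised to an arm, r the responders and m the unassessed subjects dropped.

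- Rate with everyone in the denominator: r/N
- Rate with m dropped: r/(N − m)
- Difference: r·m / [N(N − m)], which is never negative

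So dropping unassessed subjects either raises the rate above responders over randomised or leaves it unchanged. This does not carry over to every undosed or mis-dosed subject. An undosed subject who responded to chemotherapy would be lost from numerator and denominator alike, which can lower the rate, and regrouping can move it either way.

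Inputs: 15 randomised subjects (SAP 4.2). The documents give no arm split, so 7 and 8 are assumed. The values of r and m are also assumed.

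| Arm size N | Responders r | m = 0 | m = 1 | m = 2 |
|---|---|---|---|---|
| 8 | 4 | 50.0% | 4/7 = 57.1% | 4/6 = 66.7% |
| 8 | 5 | 62.5% | 5/7 = 71.4% | 5/6 = 83.3% |
| 8 | 6 | 75.0% | 6/7 = 85.7% | 6/6 = 100% |
| 7 | 5 | 71.4% | 5/6 = 83.3% | 5/5 = 100% |
| 7 | 6 | 85.7% | 6/6 = 100% | not possible |

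For N = 8 and r = 5, the differences are 5×1/(8×7) = 8.9 points and 5×2/(8×6) = 20.8 points. Across the table, one dropped subject adds about 7 to 14 points and two add about 17 to 29. With m = 0 the difference is zero.

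These differences come from the denominator rule, not from choosing the Safety Set as such. The population choice adds to them only through undosed subjects, and the grouping only through mis-dosed ones.

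**The case against.** The other side has a good deal to say.

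- *The departure is disclosed.* Section 6.4 names its population and gives a reason. Section 5.1 calls ITT the primary population, which does not exclude others, and may be left over from the full design. This stands: it is an open departure that needs reconciling, not a hidden contradiction.
- *The data remain visible.* Listing 6 shows response by subject, and Appendix A has listings cover all enrolled subjects. Headers carry the analysis-set N, and each module must indicate how many subjects contribute. This stands too. A reader might infer that Table 4 is the only efficacy information in the report, but it is only the only efficacy summary table.
- *The denominator loss is inferred.* It follows from a general convention, and a shell with a 'not assessed' row would remove it. True, but the SAP specifies no such row.
- *As-treated grouping is not settled.* A reader of 5.2 might conclude that Table 4 is grouped by treatment received. Section 6 supports the opposite reading. What can be shown is the ambiguity.
- *Missing need not mean failed.* It is tempting to say that the dropped subjects are mainly poor outcomes. Nothing in the documents supports that. The sponsor ended the study for business reasons (SAP Section 2), so some assessments may be absent for administrative reasons, and counting those subjects as failures could understate response. The protocol's failure rules were written for the primary endpoint and extend to CR rate only by analogy. SAP 6.4 and Section 8 also drop those endpoint analyses.

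These arguments limit the importance of the point. They do not supply the missing denominator rule or say which grouping applies.

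**Conclusion.** The point holds in a limited form. Table 4 departs from the population that SAP 5.1 names for efficacy, its grouping is ambiguous between 5.2 and Section 6, and nothing keeps unassessed subjects in its denominator. Followed as written, it can show a rate above responders over randomised subjects.

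The documents do not show that it will. They give no arm split and no counts of undosed, unassessed or mis-dosed subjects. If there are none, the Safety Set and ITT versions are identical. The 62.5%, 71% and 83% figures are an illustration for an assumed arm of 8 with 5 responders, not an estimate of bias. Nor is responders over randomised automatically the true response rate, since subjects cut off by the termination are not known failures. It is the denominator that is fixed by the randomisation and leaves nobody out.

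Impact is low: one descriptive table, 15 subjects, no inference, and a listing behind it. The change is still worth making because it is specific and cheap.

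**What to change.** 1. Present Table 4 on the ITT Analysis Set, by randomised arm, with the number randomised to each arm as the denominator.
2. Show every response category in SAP 4.4.4, plus a 'not assessed' row. Split that row into death or early discontinuation, and assessment not reached because the sponsor ended the study. Show the two separately, so that administratively unassessed subjects are not silently labelled as treatment failures.
3. Keep the Safety Set version, if wanted, as a supplement labelled as matching the DMC output, with its grouping rule stated. State which definition of treatment group, 5.2 or Section 6, governs it.
4. Correct 4.4.6: either remove its reference to 6.4 or put the handling of missing response in 6.4.

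The cost is one table re-specified for 15 subjects and a few SAP sentences. No new data are needed.

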6.5. SAFETY ANALYSIS

Descriptive summaries will be generated for safety data including TEAEs as well as changes from baseline in laboratory assessments (figure only), and graded laboratory toxicities. All adverse events will be graded for severity using NCI-CTCAE as follows:

- Grade 1 (Mild): asymptomatic or mild symptoms; clinical or diagnostic observation only; intervention not indicated
- Grade 2 (Moderate): minimal, local, or non-invasive intervention indicated; limiting age-appropriate instrumental activities of daily living (ADL)
- Grade 3 (Severe): Medically significant but not immediately life-threatening; hospitalization or prolongation of hospitalization indicated; disabling; limiting self-care ADL
- Grade 4 (Life-threatening): Urgent intervention indicated required to remove or abrogate risk of death
- Grade 5: Death related to AE

6.5.1. Adverse Events

Adverse events will be mapped to the MedDRA version in effect at the time of database lock. TEAEs will be summarized by treatment group using system organ class and preferred term.

If a subject experiences multiple events that map to a single preferred term, the event of greatest severity will be assigned to the preferred term for the appropriate summaries. Subjects with events mapping to multiple preferred terms within the same system organ class will be counted once at the system organ class level.

Separate summaries for treatment-emergent serious adverse events (TESAEs), TEAEs by severity, TEAEs related to study medication, TEAEs leading to ENTO/placebo dose reduction, interruption, discontinuation, and TEAEs with an outcome of death will be generated.

Missing onset dates will be imputed as previously outlined in [Section 4.4.4.4](#).

6.5.2. Clinical Laboratory Assessments

Laboratory toxicities will be graded for severity using NCI-CTCAE Version 5.0 (see section [Appendix B](#) for more details about laboratory grading). The frequency and percentage of subjects experiencing treatment-emergent toxicities will be summarized by treatment group. Shifts from baseline toxicity grades to worst post-treatment toxicity grades will be presented by treatment group.

Figures of observed values by study visit will be produced for the following hematology and clinical chemistry parameters of interest: hemoglobin, white blood cells, lymphocytes, ANC, platelets, alanine aminotransferase, aspartate aminotransferase, alkaline phosphatase, total bilirubin, direct bilirubin, indirect bilirubin, creatinine, urea nitrogen, percent leukemic blasts, and lactate dehydrogenase.

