6.5.1 ENTO/Placebo

Hematologic toxicity: There will be no dose modifications for hematologic toxicity except in subjects who achieve a CR with count recovery followed by recurrence of cytopenias that are not attributable to subsequent chemotherapy or other causes. In this setting, performance of a bone marrow aspirate and/or biopsy to confirm AML has not recurred is mandated. Interrupt study medication for Grade 4 neutropenia or thrombocytopenia attributed to study medication until counts return to Grade 2 or better. Study medication may then be restarted at a 50% reduced dose twice daily. If Grade 4 neutropenia or thrombocytopenia recurs, the total daily dose may be further reduced to 50% once daily. No further dose level reductions beyond this are permitted and subjects should be removed from study medication if Grade 4 neutropenia or thrombocytopenia recurs. If blood counts remain stable for 1 month after dose reduction, investigators may attempt to increase the dose of study medication by one dose level.

Dose modifications for non-hematologic toxicities are described in [Table 6](#).

CONFIDENTIAL

Protocol KB-ENTO-3001 v4.0 Global
(Amendment 3.0 Global)**Table 6: Study Treatment Modifications for Non-hematologic Toxicities**

Liver function abnormalities:	
 For Grade 1-2 abnormalities, continue study medication at full dose. For Grade ≥ 3 AST/ALT elevations, interrupt study medication and recheck transaminase levels at least weekly. When AST, ALT levels return to Grade 1 or baseline, restart study medication at a 50% reduced dose twice daily. If there is no recurrence of Grade ≥ 3 transaminase elevation after 2 weeks of reduced dose, escalation to full dose may be attempted. For Grade ≥ 3 increased blood bilirubin not attributed to increased indirect bilirubin levels, or liver function abnormalities that meet the criteria for Hy's law**, permanently discontinue therapy. 
Note: ENTO is an inhibitor of UGT1A1 and reversible increases in unconjugated (indirect) bilirubin values have occurred in healthy subjects receiving ENTO. In the absence of symptoms or other liver function abnormalities, study medication dose modification is not required for elevated indirect bilirubin levels.

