8.0 Study Assessments and Procedures

The schedule of study assessments and procedures is summarized in [Table 7](#).

All study visits should be scheduled relative to the C1D1 date regardless of any treatment interruptions. Acceptable windows for study visits/assessments after C1D1 are \pm 1 day. Unscheduled study visits may be required as clinically indicated for evaluation of AEs or suspected leukemic relapse/progression. Results of diagnostic evaluations performed as part of an unscheduled study visit must be entered into the Unscheduled Visit eCRF.

CONFIDENTIAL

Protocol KB-ENTO-3001 v4.0
(Amendment 3.0)

Table 7: Schedule of Assessments and Procedures

Study Phase	Screening	Induction (up to 2 Cycles)*					At Recovery of Blood Counts/Assessment of Remission Status (Post-Induction Cycle 1, Post-Chemotherapy Cycle 2)/At Relapse	Consolidation (up to 3 Cycles)*				End-of-Study Treatment	Long-Term Follow-up ^x
Study Visit Day ^a	-14 to 0	1	3	7	14	15 until blood count recovery		1	3	5	28 to 35	30 ± 7 days after last study treatment	
Informed consent	X												
IxRS registration/randomization	X												
Medical/smoking history/prior medications/AML baseline characteristics ^b	X												
Safety assessments													
Vital signs ^c	X	X	X	X	X			X	X	X	X	X	
Physical examination ^d	X	X			X		X	X			X	X	
Height/weight ^e	X			X				X				X	
ECG ^f	X												
ECHO/MUGA ^g	X											X	
ECOG PS (Appendix 6)	X	X			X						X	X	
AEs/concomitant medications ^h	X	X	X	X	X			X	X	X	X	X	
Hematology ⁱ	X	X	X	X	X	X	X	X		X	X		
Clinical chemistries/LFTs ^j	X	X	X	X	X		X	X		X	X		
Coagulation ^k	X	X	X	X	X								
Urinalysis ^l	X												
β -HCG/FSH ^m	X	X						X				X	
HBV/HCV/HIV serologies ⁿ	X												

CONFIDENTIAL

Protocol KB-ENTO-3001 v4.0
(Amendment 3.0)

Study Phase	Screening	Induction (up to 2 Cycles)*				At Recovery of Blood Counts/Assessment of Remission Status (Post-Induction Cycle 1, Post-Chemotherapy Cycle 2)/At Relapse	Consolidation (up to 3 Cycles)*			End-of-Study Treatment	Long-Term Follow-up ^x
Study Visit Day^a	-14 to 0	1	3	7	14	15 until blood count recovery		1	3	5	28 to 35
Induction therapy											
Study medication (ENTO/Placebo) ^o						→	X				
Cytarabine				→							
Daunorubicin or Idarubicin			→								
Consolidation therapy											
Study medication (ENTO/Placebo) ^p								→			
Age-adjusted, high-dose cytarabine								→			
Bone marrow evaluations											
Aspirate ^q	X						X				

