9.4.4 Safety Analysis

All safety analyses will be conducted on the Safety Analysis Set.

Treatment-emergent adverse events (TEAEs) defined as all events beginning or worsening from Cycle 1, Day 1 through 30 days following study treatment completion, will be coded according to the most current version of the Medical Dictionary for Regulatory Activities (MedDRA) and will

CONFIDENTIAL

Protocol KB-ENTO-3001 v4.0

(Amendment 3.0)

be summarized by treatment group, system organ class, and preferred term. Unless otherwise specified, only TEAEs will be reported in safety summaries and listings.

Additional summaries by seriousness, severity, causality, and outcomes will also be prepared. Adverse events leading to ENTO dose reduction or discontinuation as well as those with an outcome of death will be summarized with descriptive statistics. Changes from baseline in selected laboratory assessments of interest will be summarized by treatment group and severity grade.

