2.2. Schedule of Assessments

Study Phase	Screening	Induction (up to 2 Cycles)*					At Recovery of Blood Counts/Assessment of Remission Status (Post-Induction Cycle 1, Post-Chemotherapy Cycle 2)/ At Relapse	Consolidation (up to 3 Cycles)*				End-of-Study Treatment	Long-Term Follow-up ^x
Study Visit Day ^a	-14 to 0	1	3	7	14	15 until blood count recovery		1	3	5	28 to 35	30 ± 7 days after last study treatment	
Informed consent	X												
IxRS registration/ randomization	X												
Medical/smoking history/ prior medications/AML baseline characteristics ^b	X												
Safety assessments													
Vital signs ^c	X	X	X	X	X			X	X	X	X	X	
Physical examination ^d	X	X			X		X	X			X	X	
Height/weight ^e	X				X			X				X	
ECG ^f	X												
ECHO/MUGA ^g	X											X	
ECOG PS	X	X			X						X	X	
AEs/concomitant medications ^h	X	X	X	X	X			X	X	X	X	X	
Hematology ⁱ	X	X	X	X	X	X	X	X		X	X		
Clinical chemistries/ LFTs ^j	X	X	X	X	X		X	X			X	X	

Study Phase	Screening	Induction (up to 2 Cycles)*					At Recovery of Blood Counts/Assessment of Remission Status (Post-Induction Cycle 1, Post-Chemotherapy Cycle 2)/ At Relapse		Consolidation (up to 3 Cycles)*			End-of-Study Treatment	Long-Term Follow-up ^x
Study Visit Day ^a	-14 to 0	1	3	7	14	15 until blood count recovery			1	3	5	28 to 35	30 ± 7 days after last study treatment
Coagulation ^k	X	X	X	X	X								
Urinalysis ^l	X												
β -HCG/FSH ^m	X	X						X				X	
HBV/HCV/HIV serologies ⁿ	X												
Induction therapy													
Study medication (ENTO/Placebo) ^o						→	X						
Cytarabine			→										
Daunorubicin or Idarubicin			→										
Consolidation therapy													
Study medication (ENTO/Placebo) ^p										→			
Age-adjusted high dose cytarabine									→				
Bone marrow evaluations													
Aspirate ^q	X						X						
NPMI-m MRD assessments ^r	X						X					X	X
Pharmacokinetics ^s		X	X	X				X		X			

Study Phase	Screening	Induction (up to 2 Cycles)*					At Recovery of Blood Counts/Assessment of Remission Status (Post-Induction Cycle 1, Post-Chemotherapy Cycle 2)/ At Relapse		Consolidation (up to 3 Cycles)*			End-of-Study Treatment	Long-Term Follow-up ^x
Study Visit Day ^a	-14 to 0	1	3	7	14	15 until blood count recovery			1	3	5	28 to 35	30 ± 7 days after last study treatment
Peripheral blood biomarker assessments ^t	X	X		X	X		X		X		X		
Bone marrow aspirate biomarker assessments ^u	X						X						
Pharmacogenomics (whole blood) ^v	X												

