4.4.5. Presentations by Study Visit

All study visits should be scheduled relative to C1D1 regardless of any treatment interruptions. Visits will be presented according to the visit designation as recorded in the CRF. Unscheduled and Early Termination Visits will be excluded from visit presentations. All data will be presented in data listings.

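### No planned summary measures time to ANC or platelet recovery by arm, and the planned laboratory tables and by-visit figures are insensitive to a delay

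*SAP*

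**What the plan says.** SAP 6.5.2 sets out the laboratory outputs. Treatment-emergent graded toxicities are counted by group, and "Shifts from baseline toxicity grades to worst post-treatment toxicity grades will be presented by treatment group". For the graphs, "Figures of observed values by study visit will be produced for the following hematology and clinical chemistry parameters of interest"; the list includes ANC and platelets.

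SAP 4.4.5 fixes the visit axis: "Visits will be presented according to the visit designation as recorded in the CRF", and "Unscheduled and Early Termination Visits will be excluded from visit presentations". The same section, and the opening of Section 6, promise that all data will be listed. For laboratory data, however, Section 10 names only a listing of graded abnormalities (Listing 3).

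In the schedule (SAP 2.2; Protocol Table 7), induction hematology falls on Days 1, 3, 7 and 14. It then has a column labelled "15 until blood count recovery", followed by one labelled "At Recovery of Blood Counts/Assessment of Remission Status", whose heading also covers relapse.

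Protocol 9.4.4 adds only that "Changes from baseline in selected laboratory assessments of interest will be summarized by treatment group and severity grade".

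Study drug continues while counts recover (Protocol 4.1; SAP 2.1). Protocol 6.5.1 says "There will be no dose modifications for hematologic toxicity except in subjects who achieve a CR with count recovery" and whose cytopenias then recur without another explanation. SAP 4.2 records termination at 15 randomized subjects, and SAP 4.1 and 4.4.3 rule out testing and inference.

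**The concern.** Intensive chemotherapy produces deep cytopenia in both arms, so an added marrow effect of a drug dosed through aplasia would be expected to show mainly as longer cytopenia. None of the planned laboratory displays is on a time scale that measures length. Two arms could have similar worst-grade tables and similar graphs at the recovery visit while one took a week longer per cycle to get there. That would matter for infection, bleeding and the start of consolidation. It would also matter for response, because CR requires count recovery and the assessment is capped at Day 42.

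**Working it through.** The plan states no figure on this point, so there is nothing to reproduce. The check is an inventory of outputs, followed by arithmetic on how much of a delay the indirect ones would show.

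**1. Is recovery time summarized anywhere?** SAP 6.3 to 6.5, SAP Section 10 and Protocol 9.4.4 contain no summary of days to recovery or duration of cytopenia.

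**2. Graded tables.**
- Worst grade has no time component.
- A treatment-emergent toxicity needs a shift of at least one grade (SAP 4.4.4). A subject entering with Grade 4 cytopenia cannot qualify, and in the shift table has no room to worsen.
- In SAP Appendix B, platelet Grade 1 ends at 75,000/mm³, so crossing 100 x 10⁹/L is not a boundary between numbered grades.
- Protocol Table 2 (earlier ENTO study, 53 subjects) partly supports a ceiling. Every reported case was Grade 3–4 for WBC (49 of 49), febrile neutropenia (44 of 44), platelets (41 of 41), anaemia (28 of 28) and neutrophils (19 of 19). Lymphocytes were not (17 of 34).

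**3. Figures.** The CRF is not in the documents. I assume its visit labels follow the schedule's columns. After Day 14 of induction there is then one open-ended label and one label named for recovery and shared with relapse. Neither has a fixed day. Consolidation has no column between Day 5 and Days 28–35, although counts are monitored twice weekly (Protocol 8.6.4). Counts filed as unscheduled are left out.

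**4. Indirect route: response after two cycles (Table 4, Listing 6).** CR versus CRh/CRi turns on ANC and platelets. The documents give no recovery times, so this is an assumed illustration with normal recovery times: P(T > 42) = 1 − Φ((42 − m)/σ).

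| σ (days) | m = 28 | m = 35 | Rise x 8 subjects |
|---|---|---|---|
| 5 | 0.3% | 8.1% | 0.6 |
| 7 | 2.3% | 15.9% | 1.1 |
| 10 | 8.1% | 24.2% | 1.3 |

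A lognormal shape gives a similar picture. With median 28 and log-SD 0.15 to 0.25, the share unrecovered is 0.3% to 5%; with median 35 it is 11% to 23%.

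**5. Indirect route: relative dose intensity (Table 3).** The reference is 28 days, but SAP 4.4.4 does not define duration. If it means cycle length, full dose over 28, 35 or 42 days gives 100 x 28/28 = 100%, 100 x 28/35 = 80% or 100 x 28/42 = 67%, and a delay shows. If it means dosing days, it does not.

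**6. Precision of a direct summary now.** Assume an 8 versus 7 split. The 95% half-width for a difference in mean days is t(0.975, 13) x σ x √(1/8 + 1/7) = 2.160 x 0.5175 x σ. That is 5.6, 7.8 or 11.2 days for σ = 5, 7 or 10.

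**The case against.** The strongest objection is that the trial is over. The SAP was written for an abbreviated report on 15 subjects with no inference, and at that size recovery can be read subject by subject from listings. This stands in large part. It removes any power argument and limits the point to a descriptive improvement. It does not remove the gap, because Section 10 names no full hematology listing and Protocol 9.4.4 left the same gap for the planned 180 subjects.

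A reader might infer that hematologic safety is shown only as worst grade and by-visit counts, that delayed recovery cannot appear in any output, or that the planned outputs would have essentially no power to show it. The documents do not support these readings:
- Table 4 splits CR from CRh/CRi by arm.
- Dose intensity may show delay.
- The consolidation Day 28–35 visit is a calendar window.
- Cytopenia, infection and bleeding events are tabulated by severity, seriousness, relatedness and dose action (SAP 6.5.1).
- The recovery-named column is also the remission assessment. With the Day 42 cap, and with Induction Cycle 2 allowed before recovery, some subjects plotted there will be unrecovered.

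It is also tempting to read Protocol 6.5.1 as anticipating delayed first recovery on ENTO. Its Grade 4 rule concerns cytopenias that recur after recovery in CR. Protocol 2.4 attributes rash, indirect hyperbilirubinemia and transaminase elevations specifically to ENTO, and cites no recovery-delay signal.

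The ceiling is only partly shown. Table 2 counts reported events rather than programmatic grades, and neutrophil decrease (36%) and anaemia (53%) were far from universal.

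**Conclusion.** The point holds as a gap in measurement. No planned output summarizes time to ANC or platelet recovery by arm, and the laboratory tables and figures that might be taken to cover it are insensitive to delay. What remains is indirect. On the assumptions above, a 7-day delay adds about one unrecovered subject at Day 42 in an arm of eight, and dose intensity helps only under one reading of an undefined term. The recovery times, their spread and the 8 versus 7 split are all assumed. A direct summary would also be imprecise (half-width roughly 6 to 11 days), so it describes and does not test. The case for it is that it puts existing counts and dates on the relevant scale at little cost.

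**What to change.** In SAP 6.5.2:
- Plot ANC and platelets against days since Day 1 of each chemotherapy cycle, using all recorded counts including unscheduled ones, in place of the visit label.
- Add a descriptive by-arm, per-cycle table or listing on the Safety Analysis Set of days from cycle Day 1 to first ANC >1.0 x 10⁹/L and first platelets >100 x 10⁹/L, the thresholds already used for CR. Take the first value above threshold after the cycle's nadir, since a subject may start consolidation already above it.
- Give the number unrecovered at Day 42. Flag death, persistent or recurrent leukemia, and start of the next chemotherapy before recovery.
- State that the output is descriptive.

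Separately, the platelet level for starting Consolidation Cycle 1 must be reconciled. It is >100 x 10⁹/L in Protocol 4.1 and SAP 2.1, but ≥50 x 10⁹/L in the asterisked footnote to the schedule in both documents. Until it is, the flag for the next cycle starting before recovery is hard to interpret.

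The cost is SAP wording, one output and a changed axis. No new data are needed. Induction counts between scheduled days follow institutional practice, so their spacing and CRF capture may be irregular, and recovery days will be approximate.
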